Training and Evidence Related to Child Anxiety Reduction Skills: Teachers will learn skills based on cognitive behavioral strategies (CBT) including relaxation training (to reduce physiological arousal), behavioral strategies (e.g., "exposure" or facing anxiety provoking situations which lowers anxiety via new learning), addressing maladaptive thoughts that maintain anxiety, and problem solving skills. To implement these new skills with specific children teachers will be trained to use a school-home journal that includes a type of daily report card that tracks behavioral exposures (Show That I Can or STIC tasks) and use a reward system for increasing brave behavior /adaptive coping skills.). These "common elements" of CBT are powerful agents of change and have been implemented by CBT experts and non-experts (Cartwright-Hatton et al., 2004; [name] et al., 2011; James et al., 2013). As such, these skills are established and empirically-supported; however, they have not been evaluated when delivered by teachers. Teachers will also receive training in effective classroom-based accommodations that may be needed (e.g. untimed testing) or may need to be gradually faded if they are maintaining anxiety through negative reinforcement (e.g. allowing child to avoid participating in class due to anxiety). Another component of the teacher training includes skills that teachers deliver to their classroom (i.e., such as leading the entire class in a relaxation exercise prior to an exam; teacher using a coping model or teacher reducing their accommodation of avoidant/anxious behavior for all students). Finally, teachers will be trained in how to modify their own behaviors that have been shown to increase student anxiety (e.g., hostility, over-control). These modifications are also designed to improve the quality of the teacher-student relationship. Research on the role of teacher behavior in the development and/or maintenance of child anxiety suggests that teachers who exhibit highly controlling behaviors, such as issuing frequent directives, tend to increase child anxiety and negatively affect children's ability to learn (Assor et al., 2005). Teacher-student conflict has also been associated with anxiety symptoms, such as withdrawal (Zhang, Chen & Zhang, 2008). Conversely, positive teacher-child relationships have been found to protect youth from developing internalizing behavior problems over time (O'Connor, Dearing, & Collins, 2011). Consequently, TAPES aims to modify these teacher behaviors.

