The importance of close interaction between school and home settings has been emphasized for decades and psychosocial interventions that incorporate both parent and school components have been successful in improving academic and behavioral outcomes, though the targets have primarily been externalizing behaviors (Sheridan, Clarke, & Burt, 2008). Moreover, data from school-home intervention studies reveal that improvements in teacher-reported relationships with parents mediate intervention effects on positive changes in child outcomes, highlighting the critical role of training teachers in how to develop this collaborative relationship. TAPES Training Format and Implementation: Students' primary teacher will participate in a one-day training (approximately 8 hours). One of the most important strategies for ensuring that TAPES is implemented with high fidelity is appropriate training and ongoing consultation. Training strategies will be based on published guidelines (Beidas & Kendall, 2010) and will include active/experiential learning strategies, opportunities for observation (via video clips), live modeling and role plays, and coached practice. Ongoing performance feedback and consultation has been found to enhance learning (Fixsen et al., 2005; Sholomskas et al., 2005) and is related to higher fidelity (Sholomskas et al., 2005). Thus, teachers will be offered 30-minutes of weekly consultation by Drs. [name] and [name] for each active TAPES students. Consultation will include case review, skill rehearsal, problem-solving obstacles, and feedback regarding performance based on audiotaped sessions. Meetings will be held in person, over the phone, or via Skype at times convenient for teachers. After each teacher identifies their first child, the PIs will attend one conjoint meeting in order to provide performance feedback (all conjoint meetings are audiotaped for fidelity). The PIs will also provide in classroom coaching for 30-minutes for each student enrolled. Training materials will be available on the internet or thumb drive for reference.

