Stage 1: Establish DT and refine initial version of the TAPES Protocol. The DT will strive to ensure that the teacher training will be acceptable, feasible, and usable in the school setting. DT Composition: The DT will consist of the PIs (Drs. [name] & [name]), two national experts in teacher training (Drs. [name] & [name]), two experts in school-home collaborative interventions (Drs. [name] & [name]), and two experts in training school-based personnel in CBT techniques for anxious youth (Drs. [name] and [name]). A representative from the CT Department of Education ([name]), a CT school psychologist ([name]), and two CT elementary teachers (TBN) will complete the DT. See Appendix for letters of support. DT Procedures and Analysis: DT members will be provided with all materials at least one month prior to the first meeting so they can review the initial protocol. Next, DT members will participate in a half day meeting during which the PIs will present an overview of all study components (e.g., rationale, training strategies, methods for teacher observations). The meeting will take place using an interactive web conferencing site that enables real-time Q&A. DT members will provide detailed feedback about the TAPES strategies, study methods/measures, perceived barriers to successful implementation and adoption by teachers, and solutions to potential barriers. Information from this meeting will be used to revise the protocol in preparation for the first open trial. Within four weeks, a revised version of the protocol will be distributed to the DT for another round of revisions during a second meeting. A similar procedure will be used for each successive revision of the protocol. Stage 2: Open **Trials.** During Stage 2, teachers and IEs will be trained and will conduct two sequential open trials. Study staff will engage in screening activities of students and IEs will complete baseline evaluations on referred students. The purpose of the open trials is to evaluate the feasibility of the training, modify methods as needed, allow teachers to implement the skills learned in the training and receive real time coaching and consultation with anxious children. Data on TAPES usability, acceptability, fidelity, satisfaction, and teacher and child outcomes will also be collected (see Measures below). After each open trial, feedback (via exit interviews and standardized measures) from teachers, students, and parents will be integrated by the research team and presented to the DT for another revision of the protocol. Teachers will be asked to participate in an exit interview after they implement TAPES with an anxious child. Stage 3: Pilot RCT. In stage 3, we will conduct a pilot RCT with 40 teachers and a maximum of 60 anxious youth. The RCT will be conducted in 3 phases.

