
Phase 1 - Recruitment, Randomization, Training, Student Screening, and Baseline

Evaluations: In Phase 1, teachers will be randomly selected from the pool of interested participants and randomized to TAPES or TAT. Once randomized, teachers will complete their assigned training. Teachers will then identify potentially eligible students from their classes and provide information about the study to their parents. Interested parents will contact study staff and complete a brief phone screen. Students who appear eligible based on the phone screen (e.g.,

have elevated anxiety; are in elementary school) will be invited to complete informed consent and a full baseline evaluation with an IE (see Table 1 for measures). Families who "pass" the baseline evaluation (i.e., student obtains a *t* score of 60 on Spence Children's Anxiety Scale (SCAS) and/or a CSR of at least 3 on the ADIS-V) will be considered eligible (see Inclusion/Exclusion criteria below).

Phase 2 – TAPES/TAT Implementation: Teachers will implement TAPES or TAT depending on their random assignment over 8 weeks from child enrollment.

Phase 3 - Post- and Follow-up Evaluations: At the end of the 8 weeks, teachers and children in both groups will complete a post evaluation (see Table of Measures). Teachers, students, and parents will complete a TAPES satisfaction measure and provide feedback to enhance the protocol. Teachers will complete an exit interview. Students who need mental health services will be referred to the school counselor or community provider for treatment. A 3 month follow-up evaluation to assess sustained use of TAPES/TAT skills will be conducted.

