Sub study: From an economic perspective, anxiety confers a high economic burden on the individual, state and national level. Based on data from 2002, the annual cost of anxiety disorders in the United States is likely to be more than \$100 billion. These cost estimates are 16 years old and an updated examination of the cost of pediatric anxiety disorders is needed. Research has not investigated the potential financial benefit (e.g. school attendance, standardized test scores) or fiscal feasibility of adopting these interventions relative to current practices. Within the United States, it is also uncertain whether the cost burden of pediatric anxiety varies by demographic factors (e.g. minority status, socio-economic status, gender). Each of these cost factors represent sizable gaps in scientific knowledge. In this context, a Pre-K award was submitted to the Connecticut Institute for Clinical and Translational Science in order to fill this important gap in the scientific literature. This sub study will examine the cost of pediatric anxiety and the relative benefit of TAPES compared to usual care (UC). The purpose of this costs and benefits analysis is to provide information to school system administrators and teachers regarding the budgetary consequences of pediatric anxiety and to summarize the cost of achieving potential improvements in school functioning.

Procedures for Summer Months. We will only randomize teachers and enroll students if at least 10 weeks of school remain in the academic year to allow sufficient time to complete baseline evaluation, TAPES implementation and post evaluations.

Randomization. During the RCT, randomization will occur at the teacher level at a 1:1 (20 TAPES: 20 TAT). The randomization plan will be generated prior to the identification of teachers to minimize potential biases. Randomizing teachers to two active training conditions was selected for several reasons. The current design allows for all teachers to receive some training in anxiety identification and reduction—a major recruitment barrier in our previous school-based trials where clinicians or nurses were assigned to a no training control condition and subsequently dropped from the study. In addition, this design allows for an examination of a brief teacher training which represents typical teacher professional development offerings in CT.

Participants and Recruitment

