burnout, teacher efficacy; teacher behavior) and child characteristics (e.g., gender, age, baseline anxiety symptoms, classroom functioning). To test the main hypothesis, that teachers in TAPES, compared to TAT, will have higher knowledge about anxiety reduction, we will examine scores on the *Teacher Knowledge Assessment* at post-training, and at the end of school year as outcomes in GLM controlling for teacher pre-training score. Let y_i denote the post-training or end of school year test score of teacher i, x_{i1} and x_{i2} denote teacher i's group assignment and pre-training test score, respectively, and ε_i denote resident term. Rejecting $\beta_1 \leq 0$ and $\beta_3 \leq 0$ in the model: $y_i = \beta_0 + \beta_1 \times x_{i1} + \beta_2 \times x_{i2} + \beta_3 \times x_{i1} \times x_{i2} + \varepsilon_i$ suggests that TAPES teachers' post-training test scores are higher and they have a greater gain in knowledge than TAT teachers. Teacher-specific covariates can be added to the above model as needed. To test the hypothesis that TAPES, compared to TAT, will result in greater use of anxiety reduction skills in the classroom, IE's Classroom Observation of Teachers Skills rating for each pair of teacher and anxious student at baseline, post-intervention, and 3-month follow-up will be modeled in GLMM. Now rating, y_{ijk} are nested within teacher k and student j, who is nested within teacher k, in the multilevel equations: Level 1: $y_{ijk} = \pi_{0jk} + \pi_{1jk} \times \text{timepoint}_{ijk} + e_{ijk}$; Level 2: $\pi_{0jk} = \beta_{00k} + r_{0jk}$ and $\pi_{1jk} = \beta_{10k} + r_{1jk}$; Level 3: $\beta_{00k} = \gamma_{000} + \gamma_{001} \times w_k + u_{00k}$ and $\beta_{10k} = \gamma_{100} + \gamma_{101} \times w_k + u_{10k}$; where w_k denotes teacher k's intervention-training group assignment with e, r, and u representing error terms in the respective levels. Teacher-specific (e.g., years of teaching experience, teaching efficacy) and child-specific (e.g., age, baseline anxiety severity) covariates can be added to Levels 2 and 3 equations as needed. Aim #4 (Secondary Outcomes): To examine the impact of TAPES relative to TAT on student outcomes. Change scores on student mental health (e.g., Spence Children's Anxiety Scale, SCAS) and academic achievement (e.g., Woodcock-Johnson Tests of Achievement) from pre-to postintervention and 3-month follow-up will be modeled as GLMM similar to above in Aim 3. **Exploratory aims**: To examine mediators (proposed in the theory of change, see Figure 1 in Appendix) and predictors and moderators (e.g. Teacher Background Form, MBI-Educators Scale) of TAPES impact on teacher knowledge and behavior. Structural equation modeling (SEM) will be used to explore potential predictors (e.g., baseline teacher burnout as measured by MBI-ES), mediators (e.g., subscale scores from the OSTES) and moderators (e.g., years of teacher experience) on teacher behavior change (e.g., change score on the Classroom Observation of Teachers Skills at pre-, post-intervention and 3-month follow-up). Sub study: Aim #1: Assess the direct and indirect cost of pediatric anxiety among youth enrolled in the TAPES intervention. This aim involves the modification of existing measures of direct and indirect cost. These measures will be administered to parents and teachers at existing TAPES assessment time points (i.e. baseline, post intervention and three-month follow up). Aim #1a: Estimating the cost of pediatric anxiety through direct and indirect costs. Aim #2: To examine the child and parent benefit of TAPES compared to UC. This aim involves estimating the cost of TAPES relative to the UC condition in relation to direct and indirect costs. Exploratory Aim: To examine family demographic factors as moderators of pediatric anxiety cost. **Power Analysis.** Although this is a development study proposing a small pilot RCT, attempts were made to estimate statistical power for the key outcomes based on existing literatures on similar measures (see White et al., 2011 for Teacher Knowledge Assessment and Barrett et al., 2005 for child anxiety using the SCAS). Using Optimal Design version 3.0 calculations for both variables were based on an anticipated enrollment of 20 teachers in each group (and 1-2 students per teacher). We assumed a conservative within-teacher ICC of 0.10 (Eldridge et al., 2004) and

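### A TAPES teacher's second student can be baselined after coaching on the first has begun, so the per-pair skills baseline in Aim 3 may understate change

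*Combined protocol and SAP*

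**What the plan says.** All references are to the combined protocol and SAP.

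- **Clock.** Under Phase 2 of the pilot RCT: "Teachers will implement TAPES or TAT depending on their random assignment over 8 weeks from child enrollment".
- **Size.** The RCT has "40 teachers and a maximum of 60 anxious youth". The Power Analysis assumes 20 teachers and 30 students per arm, with one or two students per teacher.
- **Enrolment limit.** Procedures for Summer Months requires at least 10 remaining weeks of school. No text requires a teacher's two students to be enrolled or baselined together.
- **Support in TAPES.** TAPES Training Format and Implementation describes weekly consultation for each active student and 30 minutes of in-class coaching for each enrolled student. It adds: "After each teacher identifies their first child, the PIs will attend one conjoint meeting in order to provide performance feedback". The TAT description is a 3-hour didactic with no such support.
- **Class-wide content.** On TAPES: "Another component of the teacher training includes skills that teachers deliver to their classroom".
- **Skills measure.** Under Primary Outcomes, the classroom observation records the teacher during ordinary lessons, not behaviour toward one child.
- **Analysis.** In Aim 3, the evaluator's "rating for each pair of teacher and anxious student at baseline, post-intervention, and 3-month follow-up will be modeled in GLMM". Aim 4 models student change scores similarly. Neither has a term for enrolment order or prior exposure.
- **Follow-up.** Phase 3 states: "A 3 month follow-up evaluation to assess sustained use of TAPES/TAT skills will be conducted".
- **Pre-training observation.** Table 1 lists one, separate from baseline, in its usability rows. The primary-outcome row and the Aim 3 model do not name it.

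**The concern.** The skills rating belongs to the teacher, but the plan resets its baseline for each child. If the second child enrols while the first is in progress or finished, the second pair's baseline shows a teacher who has already practised the skills and, in TAPES, been consulted with and coached. Part of the effect then sits in the baseline and drops out of the change. Because that support is described only for TAPES, the loss does not cancel between arms, and the time-by-arm contrast for a primary outcome shrinks.

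Two lesser consequences follow. A later-enrolled classmate may have met the class-wide strategies before baseline, which would slightly attenuate Aim 4 change scores. And the first child's follow-up observation, meant to show sustained use, could fall while the teacher is being coached on the second child, which would flatter durability in TAPES. The RCT is meant to yield a training ready for a larger efficacy trial, so either distortion could misinform that step.

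**Working it through.** **Plan's own figure.** The Power Analysis states 80% power for child anxiety at d = 0.92 with 30 students per arm, intraclass correlation 0.10 and alpha .05 (sidedness not stated; two-sided assumed). With ten teachers having one student and ten having two in each arm:

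- Design effect = 1 + (50/30 - 1) × 0.10 = 1.067, so effective n = 30/1.067 = 28.1 per arm.
- Power (normal) = Φ(0.92 × √(28.1/2) - 1.96) = 93.2%; with a t reference, 91.9%.

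The stated 80% therefore holds only as a minimum. The concern does not depend on it. The plan gives no power for the skills outcome, so only a proportional loss can be shown there.

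**How many second students.** 60 - 40 = 20 second students if the maximum is reached and every teacher enrols at least one. That is 20/60 = 1/3 overall, or 10 of 30 per arm if evenly split.

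**Attenuation.** Let Δ be the between-arm effect on change, p the share of students who are lagged second students, and f the fraction of Δ already present at their baseline. Weighting pairs equally:

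(1 - p)Δ + p(1 - f)Δ = (1 - p × f)Δ

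Neither p nor f is in the documents, so both are assumptions:

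| Lagging second students | p | f = 0.25 | f = 0.5 | f = 0.75 | f = 1 |
|---|---|---|---|---|---|
| All 20 | 1/3 | 91.7% | 83.3% | 75.0% | 66.7% |
| Half (10) | 1/6 | 95.8% | 91.7% | 87.5% | 83.3% |
| None | 0 | 100% | 100% | 100% | 100% |

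The mixed model will not weight pairs exactly equally, so these are approximate.

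**Student outcomes.** Taking p = 1/3, power for child anxiety falls from 93.2% to 88.5% at f = 0.25 (effect 0.84) and 82.0% at f = 0.5 (effect 0.77). At f = 1 it would be 63.3%.

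**Follow-up timing.** Assume follow-up is 3 months (about 13 weeks) after the 8-week post visit. The first child's follow-up is then at week 8 + 13 = 21. A second child enrolled at week s is active from s to s + 8.

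- The visit falls in that window when s ≤ 21 ≤ s + 8, that is, s from about 13 to 21 weeks.
- With the 10-week rule, s = 13 needs at least 13 + 10 = 23 school weeks left when the first child enrols.
- A shorter lag still puts coaching inside the 8-to-21-week interval, but not at the visit.

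**The case against.** The strongest reply is that staggered entry is not stated. The phrase about a teacher's first child only identifies the case for which the investigators attend a meeting. Consultation for each active student fits two concurrent students equally well. Phase 1 places recruitment and baseline evaluation before Phase 2 implementation. This stands: the plan permits staggering but does not say it is expected. It does not close the gap, because the phases are not said to apply to all of a teacher's students together, and the Child Recruitment section foresees recruitment continuing past its first 2 months, about one implementation period.

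A reader might also infer more than the documents support:

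- **That one third of pairs are affected.** This is a ceiling. It needs 60 students, at least one per teacher, and every second student lagging.
- **That student outcomes suffer equally.** Most child-level content is individual (fear hierarchies, exposure tasks, school-home journal, conjoint meetings), and a second child has had none of it before enrolment. That child must also meet the anxiety threshold at their own baseline. Only class-wide strategies and general teacher behaviour carry over, so f is probably small and the 63.3% power figure is not a realistic expectation.
- **That the sustained-use follow-up is generally invalid.** Only a lag of about 13 to 21 weeks puts the visit inside active coaching.

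Finally, even first-student baselines follow teacher training in both arms. That is a wider weakness of the skills baseline. It does not remove this one, since coaching and practice come later, but it bears on the choice of remedy.

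**Conclusion.** The point holds as a gap the plan leaves open, not as a bias shown to occur. For lagged second students in TAPES, the per-pair skills baseline follows support not described for TAT, and baseline-to-post change in teacher skills is pulled toward zero. The estimated effect is (1 - p × f) of the true one: from no loss, if students enrol together, to two thirds of the effect at the extreme. The result assumes a beneficial TAPES effect and little comparable carry-over in TAT. Any attenuation of Aim 4 should be smaller. The follow-up distortion runs the other way, toward overstated durability, and needs a particular lag. Teacher knowledge is not exposed to this problem, because it is a teacher-level score adjusted for the pre-training score.

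**What to change.** - **Aim 3 skills model.** Use one baseline per teacher, the pre-training classroom observation, instead of a new baseline for each pair. This also avoids the post-training baseline of first students. Name it in the Aim 3 model and the primary-outcome row of Table 1, and confirm that it is done in both arms.
- **Aim 4.** Record enrolment order and the lag between a teacher's students. Add a first-student-only or order-adjusted sensitivity analysis.
- **Follow-up.** Flag observations made while the teacher has another active student, and report sustained use with and without them.

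The cost is slightly more analysis work and lower precision in the first-student-only analysis. With 20 students per arm and d = 0.92, its power is Φ(0.92 × √(20/2) - 1.96) = 82.9% (normal) or 80.9% (t), still above the plan's 80%.

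The plan should not hold back a first child's start until a second is baselined, or move follow-up visits later. The first delays a child for a second who may never enrol, and the 10-week rule leaves only about 2 weeks beyond the 8 of implementation. The second could push observations past the school year.
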